3.1 Study design

The present cross-over randomised clinical trial follows the Consolidated Standards of Reporting Trials (CONSORT) [Kaynak] guidelines and was performed at Marmara University, School of Dentistry, Department of Pediatric Dentistry clinics (Türkiye). The trial complies with the requirements set forth by the World Health Organization (WHO) and the International Committee of Medical Journal Editors (ICMJE).

3.2 Study population

The study population consisted of 28 children, aged 6 to 12 years of both genders who met the criteria were recruited for the study. The inclusion criteria were; children with good general health without any history of allergic reactions as determined by a written history; not currently taking any analgesics or sedative medication that would alter their pain perception; children demonstrated either 'positive' or 'definitely positive' behaviour according to the Frankl Behavior Scale (FBS); requiring treatment on their maxillary primary molars bilaterally with similar operative difficulties. The exclusion criteria were the existence of medical or developmental situations, history of chronic disease, 'negative' or 'definitely negative' behavior rating according to the Frankl Behavior Scale (FBS), and the presence of inflammation at the injection site.

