3.3 Procedure

The study was conducted by two expert pediatric dentists. One of them gave all explanation, spoke with the children and carried out the anesthesia procedure and did the treatment procedure [name] and the other [name] was observing and assessing the children's pain perception.

In this study's cross-over design, children received both types of injections before filling/pulpotomy treatment on their maxillary primary molars in two separate appointments with a minimum interval of at least 1 week between procedures, on a side of the dental arch with the use of a needle free injection and on the other side with the traditional syringe. Type and sequence of administration to each individual were randomly assigned (using a coin). All dental equipment were introduced using 'tell-show-do technique. A total of 56 procedures were performed and divided into 2 groups according to the anesthesia technique. None of the children have undergone any previous dental local anesthetic experience, in order to be not influenced by a positive or negative memory.

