3.3.1 Injection with the needle-free (NF) system

The device used for needle free system was **Comfort-in™** (Mika Medical Global Co, Busan, Korea) anesthesia device (Figure 1). The **Comfort-in™ system**, has a micro-hole injection needle (0.15 mm) that injects the anesthetic solution under the mucosa. The pressure can be controlled according to the dose of the drug to be used, thereby reduced the pain that may occur with the needle in the injection. Before the injection procedure, the children were demonstrated the popping sound produced by device to prevent reflex reactions, and they informed that they would feel as if their gum were punched. The NF injection device was prepared according to the manufacturer's instructions, placed in full contact with the buccal mucosa and a pre-withdrawn dose of 0.1 ml was applied to the buccal region for topical purposes by the pushing the top of the device. After 10-15 seconds, the same procedure was repeated with withdrawn dose of 0.3 ml. After 5 min the treatment commenced, and the children were instructed to raise their hand if they experienced pain during the procedure. Each time the child indicated pain, in accordance with the same protocol an additional 0.3 ml of anesthetic solution was administered, until the sufficient anesthetic effect was obtained and the final amount of anesthetic solution

The Effect of Needle-free Injection System on Dental Injection Pain in Children: A Cross-over, Randomized Clinical Trial

were recorded. Precautions were taken to prevent tissue ballooning. After the treatment, duration of the analgesia effect (min) were also recorded. The presence of post-operative pain in patients was assessed via a phone call 1 day after the procedure.

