3.4 Data collection

A structured form was designed to collect information regarding

- (1) patient's age;
- (2) gender;
- (3) type of teeth injected
- (4) type of dental treatment (filling or pulpotomy);
- (5) total amount of local anesthetics (LAs) used (ml)
- (6) duration of the analgesia effect (min)
- (7) post-op pain (after one day)
- (8) score on WB PRS after injection
- (9) score on FLACC during injection.

The Effect of Needle-free Injection System on Dental Injection Pain in Children: A Cross-over, Randomized Clinical Trial

Statistical Analysis

Post hoc power analysis was conducted for the study and the results of the comparison between the injection systems and Wong Baker scores were evaluated. According to this, with a total data set of 28 individuals, consisting of two independent groups and two dependent measurements, the power of the study was found to be 0.94 according to the G*Power 3.9.1.4 program, based on the partial eta squared (η^2) value of 0.108 obtained with a 0.05 error margin from the repeated measures ANOVA. The data were statistically analyzed using SPSS software (version 15.0, SPSS). Paired t-tests or Wilcoxon nonparametric tests were used to compare data within groups over two time periods, according to check the distribution whether normally distributed or not. The Chi-square test (X^2 -test) was also used to compare discrete random variables. Spearman's Rho correlation coefficient was used to find any relationship between two continuous variables. A p-value ≤ 0.05 was considered statistically significant.

4. Results

Total of 28 children, consisting of 18 girls (64.3%) and 10 boys (35.7%) aged 6–12 years were involved in this study. Mean age was 8.07 years with a standard deviation of 1.41 years. At the end of this study, a total of 56 injections were obtained for 28 children as NF injection (n = 28) and TM injection (n = 28).

In the study, when the distributions of the parameters (gender, type of dental treatment, type of teeth, and post-operative pain) were evaluated according to the type of injection technique, it was found that there was no statistically significant difference between the groups. (Table 1)

Table 1. Distribution of injection techniques based on evaluation parameters

Variables		Needle Free (NF) n	Traditional Method (TM) n	Total	p
Gender	Girl	18	18	36	1,000
	Boy	10	10	20	
Type of dental treatment	Filling	22	14	36	0,051
	Pulpotomy	6	14	20	
Type of teeth injected	1 st primary molar	12	7	19	0,259

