in different sequences over two sessions. The analysis showed no statistically significant differences between the groups (Table 3). Similarly, present study evaluated the impact of the type and sequence of restorations (filling-filling, filling-pulpotomy, pulpotomy -filling) on Wong-Baker and FLACC scores for needle-free and traditional method injections administered in different sequences over two sessions. Results demonstrated that there were no statistically significant differences between the groups (Table 4).

Table 4: Wong-Baker and FLACC Scores in Needle Free-Traditional Method and Traditional Method - Needle Free groups based on type of dental treatment

	Type of Dental Treatment	Needle Free-Traditional Method Group		p	Type of Dental Treatment	Traditional Method-Needle Free Group		p
		1 st visit Needle Free	2 nd visit Traditional Method			1 st visit Traditional Method	2 nd visit Needle Free	
Wong Baker	Filling-Filling N=4	7, (3-9.5)	2, (0.5-2)	0,109	Filling-Filling N=8	2, (0.5-2)	2, (0.5-5.5)	0,167
	Filling-Pulpotomy N=3	4, (2-4)	2, (0-2)	0,180	Filling-Pulpotomy N=2	0, (0-0)	1, (0-1)	0,317
	Pulpotomy-Filling N=2	1, (0-1)	2, (2-2)	0,317	Pulpotomy-Filling N=9	2, (0-3)	2, (0-4)	0,655
FLACC	Filling-Filling N=4	0.5, (0-2.5)	0, (0-0)	0,180	Filling-Filling N=8	0, (0-0)	1, (0-1)	0,096
	Filling-Pulpotomy N=3	1, (0-1)	0, (0-0)	0,180	Filling-Pulpotomy N=2	0, (0-0)	0.5, (0-0.5)	0,317
	Pulpotomy-Filling N=2	0, (0-0)	0.5, (0-0.5)	0,317	Pulpotomy-Filling N=9	0, (0-1)	1, (0-1)	0,257

*Wilcoxon nonparametric test was used

*Needle Free-Traditional Method group: 1st visit Needle Free and 2nd visit Traditional Method was used for injection.

*Traditional Method - Needle Free group: 1st visit Traditional Method and 2nd visit Needle Free was used for injection

*The values are presented as Median, (Inter Quartile Range)

*filling-filling group: 1st visit filling and 2nd visit filling restoration have been done

*filling-pulpotomy group: 1st visit filling and 2nd visit pulpotomy restoration have been done

*pulpotomy-filling group: 1st visit pulpotomy and 2nd visit filling restoration have been done

Table 5. Amount of Anesthetic Solution (ml) in Needle Free-Traditional Method and Traditional Method - Needle Free groups based on type of dental treatment

	Type of Dental Treatment	Needle Free-Traditional Method Group		p	Type of Dental Treatment	Traditional Method-Needle Free Group		p

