		1 st visit Needle Free	2 nd visit Traditional Method			1 st visit Traditional Method	2 nd visit Needle Free	
Amount of Anesthetic Solution (ml)	Filling-Filling N=4	0.65, (0.325-1.125)	1.3, (1.05-1.85)	0,068	Filling-Filling N=8	1.1, (1-1.85)	0.55, (0.325-0.9)	0,012
	Filling-Pulpotomy N=3	0.9, (0.3-0.9)	2, (1.5-2)	0,180	Filling-Pulpotomy N=2	1.4, (1.3-1.4)	1, (1-1)	0,180
	Pulpotomy-Filling N=2	1.35, (1.2-1.35)	1.75, (1.5-1.75)	0,180	Pulpotomy-Filling N=9	1.5, (1.1-1.85)	0.6, (0.3-0.9)	0,008

*Wilcoxon nonparametric test was used

*Needle Free-Traditional Method group: 1st visit Needle Free and 2nd visit Traditional Method was used for injection.

*Traditional Method - Needle Free group: 1st visit Traditional Method and 2nd visit Needle Free was used for injection

*The values are presented as Median, (Inter Quartile Range)

*filling-filling group: 1st visit filling and 2nd visit filling restoration have been done

*filling-pulpotomy group: 1st visit filling and 2nd visit pulpotomy restoration have been done

*pulpotomy-filling group: 1st visit pulpotomy and 2nd visit filling restoration have been done

Table 5 showed the evaluation whether the type and sequence of different restorations administered in different sequences over two sessions with needle-free and traditional method

10.04.2017

The Effect of Needle-free Injection System on Dental Injection Pain in Children: A Cross-over, Randomized Clinical Trial

injections resulted in any differences in the amount of anesthetic solution used. The results indicated a significant difference in the amount of anesthetic solution used in the group that received TM injection in the first session and NF injection in the second session, the group that received filling in both the first and second sessions, and the group that received pulpotomy in the first session and filling in the second session. A significantly lower amount of anesthetic solution was used in the NF injection in both groups (Table 5).

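### The volume saving reported for needle-free injection is partly confounded by procedure: 16 of 28 children had a filling on one side and a pulpotomy on the other, and in 12 of the 16 the pulpotomy was under the traditional method

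*Combined protocol and SAP*

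**What the plan says.** Section 3.2 makes comparability of the two sides an entry condition: "requiring treatment on their maxillary primary molars bilaterally with similar operative difficulties". It does not define similar. Section 3.3 names two treatments and has no rule that both sides receive the same one: "children received both types of injections before filling/pulpotomy treatment on their maxillary primary molars in two separate appointments".

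Sections 3.3.1 and 3.3.2 apply the same top-up rule under both techniques: "Each time the child indicated pain, in accordance with the same protocol an additional 0.3 ml of anesthetic solution was administered". The recorded total therefore accrues partly during the operative work.

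Tables 4 and 5 divide the children by procedure pair within each sequence. The labels follow visit order, for example "pulpotomy-filling group: 1st visit pulpotomy and 2nd visit filling restoration have been done". Table 2 compares amounts within each sequence by paired t-test, with no account of procedure. The Statistical Analysis section names no procedure-adjusted comparison of amount. Of two significant Table 5 strata, the text says: "A significantly lower amount of anesthetic solution was used in the NF injection in both groups (Table 5".

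**The concern.** In a split-mouth crossover the child is a fair control for himself or herself only if the two sides differ in technique alone. If one side has a pulpotomy and the other a filling, a volume titrated to pain during treatment reflects both technique and procedure. Table 5 suggests that it does: in each of the four technique-by-sequence columns the pulpotomy cell has the highest median.

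- NF, visit 1: 1.35 ml, against 0.65 and 0.9 for fillings
- TM, visit 2: 2.0 ml, against 1.3 and 1.75
- TM, visit 1: 1.5 ml, against 1.1 and 1.4
- NF, visit 2: 1.0 ml, against 0.55 and 0.6

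If pulpotomies fall mainly on the TM side, the apparent saving with NF is too large. What is at stake is the size of that saving and the reading of one subgroup p-value. Wong-Baker is rated straight after the injection and FLACC during it, so the pain scores are much less exposed.

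**Working it through.** **1. The document's own balance check.** Table 1 gives "Filling 22 14 36 0,051" and "Pulpotomy 6 14 20" (NF, TM, total). With Yates correction, chi-square = 56 × (|22×14 − 14×6| − 28)² / (36×20×28×28) = 3.81, p = 0.051, which reproduces the stated value. Uncorrected, p = 0.026; Fisher's exact test gives 0.0496. All three treat 56 paired injections as independent.

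**2. Procedure pairs (Table 4) and median volumes (Table 5), in ml.**

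| Sequence | Pair | N | TM | NF | TM − NF | Pulpotomy side |
|---|---|---|---|---|---|---|
| NF-TM | filling-filling | 4 | 1.3 | 0.65 | 0.65 | none |
| NF-TM | filling-pulpotomy | 3 | 2.0 | 0.9 | 1.1 | TM |
| NF-TM | pulpotomy-filling | 2 | 1.75 | 1.35 | 0.4 | NF |
| TM-NF | filling-filling | 8 | 1.1 | 0.55 | 0.55 | none |
| TM-NF | filling-pulpotomy | 2 | 1.4 | 1.0 | 0.4 | NF |
| TM-NF | pulpotomy-filling | 9 | 1.5 | 0.6 | 0.9 | TM |

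Discordant pairs: 3 + 2 + 2 + 9 = 16 of 28 (57%). Pulpotomy under TM: 3 + 9 = 12; under NF: 2 + 2 = 4. The exact McNemar test for 12 against 4 is 2 × P(X ≥ 12 | 16, 0.5) = 0.077.

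**3. Size of the distortion (N-weighted differences in medians).**

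- Filling-filling: (4×0.65 + 8×0.55)/12 = 0.58 ml
- Pulpotomy under TM: (3×1.1 + 9×0.9)/12 = 0.95 ml
- Pulpotomy under NF: (2×0.4 + 2×0.4)/4 = 0.40 ml
- All 28: (7.0 + 11.4 + 1.6)/28 = 0.71 ml

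The overall figure is close to the Table 2 mean differences, 1.62 − 0.91 = 0.71 and 1.37 − 0.65 = 0.72 ml. Against filling-filling pairs, the mix adds about 0.71 − 0.58 = 0.13 ml. As a rough cross-check, weighting the two discordant types equally cancels the procedure effect if that effect is additive: (0.95 + 0.40)/2 = 0.675 ml, an inflation of about 0.04 ml. This second figure leans on four children.

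**4. The two significant strata.** If every difference has the same sign, the asymptotic Wilcoxon p-value reaches its floor, with z = [n(n+1)/4] / √[n(n+1)(2n+1)/24]. For n = 8, z = 18/√51 and p = 0.012; for n = 9, z = 22.5/√71.25 and p = 0.008. These equal the printed values, so the smaller p in the pulpotomy-filling stratum reflects one more child and is not stronger evidence. The floor for n = 4 is 0.068, also as printed. These p-values fit all 12 children listed as filling-filling having used less under NF.

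**5. Conflict between tables.** Table 1 has 6 NF and 14 TM pulpotomies; Table 4 implies 4 and 12. With k children having two pulpotomies, the Table 1 margins give 14 − k with a pulpotomy under TM only, 6 − k under NF only and 20 − 2k discordant. That is 8 to 20 children as k runs from 6 to 0, always with an excess of 8 on the TM side. If k = 2, with both children sitting in the filling-filling cells, the tables agree: 16 and 12 stand, and true filling-filling pairs fall from 12 to 10.

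**The case against.** The strongest reply is that the saving does not depend on the mix. NF has the lower median in all six strata, including the two where the pulpotomy was on the NF side (1.35 against 1.75 and 1.0 against 1.4 ml) and the mix works against NF. Filling-filling in the TM-NF sequence is significant alone (p = 0.012). The main volume result is Table 2; the p = 0.008 stratum is only a subgroup. All of this stands. A reader might infer that the volume finding is an artefact of procedure, and the documents do not support that.

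A reader might also infer that the 16 children were ineligible. That is not shown either: section 3.2 leaves similar undefined and section 3.3 openly allows both treatments.

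It can further be said that the imbalance is disclosed in Table 1, that type and sequence were assigned by coin, and that 12 against 4 is compatible with chance. True, but a chance imbalance in a factor tied to the outcome still shifts the estimate, and a non-significant test on 28 children does not establish balance. Disclosure also does not remove the p = 0.008 stratum from the evidence offered for NF.

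Finally, the medians come from cells of 2 to 9 children. In the two large TM-NF strata the interquartile ranges nearly coincide (TM 1.1-1.85 and 1-1.85; NF 0.3-0.9 and 0.325-0.9). The contrast of 0.9 with 0.55 ml should therefore not be pressed.

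**Conclusion.** The concern holds as one of size, not direction. The unadjusted volume difference in Table 2 mixes technique with procedure: 12 of 28 pairs (43%) set NF filling against TM pulpotomy, 4 (14%) the reverse, and 12 (43%) are listed as filling against filling. The inflation is roughly 0.13 ml on about 0.71 ml, and perhaps as little as 0.04 ml. The p = 0.008 result does not isolate the technique, because every child in that stratum had the pulpotomy under TM and the filling under NF.

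The figures assume that Table 4 is correct and that differences between medians stand in for paired differences, which the documents do not give. If double-pulpotomy children sit among the filling-filling cells, the 0.58 ml benchmark changes too.

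Duration and day-1 pain arise after treatment, so bias from procedure is plausible there. Neither is reported by procedure, and it cannot be quantified.

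**What to change.** 1. Before any re-analysis, reconcile the pulpotomy counts in Table 1 (6 NF, 14 TM) and Table 4 (4 NF, 12 TM) against the data forms, and correct whichever table is wrong.
2. Analyse amount with a paired model on all 28 children, with technique, procedure on each side, sequence and period. Period belongs in the model because pulpotomies also cluster by visit: by Table 4, 2 + 9 = 11 at visit 1 and 3 + 2 = 5 at visit 2. Report the confirmed same-procedure pairs as a sensitivity analysis. Making them the main set would drop 16 randomised pairs and rest on a grouping still in doubt.
3. Do the same for duration. For day-1 pain (5 events under NF, 7 under TM) go only as far as the numbers allow; counts by procedure pair may be all they support.
4. Stop citing p = 0.008 in the text under Table 5 as evidence of a technique effect, and state that the size of the volume saving depends on the procedure mix.
5. Describe the 16 children as having discordant procedures, not as failing the criterion in section 3.2. Enrolment is complete, so rewriting that criterion now would misdescribe who was recruited.

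The cost is a modest re-analysis of data already held. The stated volume difference will probably be somewhat smaller and less precise, and only four children in Table 4 with the pulpotomy under NF alone inform the reverse contrast.

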3.3 Procedure

The study was conducted by two expert pediatric dentists. One of them gave all explanation, spoke with the children and carried out the anesthesia procedure and did the treatment procedure [name] and the other [name] was observing and assessing the children's pain perception.

In this study's cross-over design, children received both types of injections before filling/pulpotomy treatment on their maxillary primary molars in two separate appointments with a minimum interval of at least 1 week between procedures, on a side of the dental arch with the use of a needle free injection and on the other side with the traditional syringe. Type and sequence of administration to each individual were randomly assigned (using a coin). All dental equipment were introduced using 'tell-show-do technique. A total of 56 procedures were performed and divided into 2 groups according to the anesthesia technique. None of the children have undergone any previous dental local anesthetic experience, in order to be not influenced by a positive or negative memory.

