	2 nd primary molar	16	21	37	
Post-op pain (after one day)	Pain	5	7	12	0,746
	No pain	23	21	44	

*The Chi-square test (X^2 -test) was also used to compare discrete random variables.

Accordingly Table 2, in the group that received Needle-Free anesthesia in the first session and Traditional Method in the second session, the Wong-Baker scores were 4.44 ± 3.28 and 1.55 ± 0.88 , respectively. On the other hand, in the group that received Traditional Method anesthesia in the first session, the WB score was 1.68 ± 1.91 , while in the Needle-Free anesthesia group, the WB score was 2.52 ± 2.56 . In both cases, regardless of the method of anesthesia applied first, no statistically significant difference was found in the two groups. In the FLACC scores, for the Traditional Method - Needle Free group significant change was observed ($p = 0.025$) while for the Needle Free- Traditional Method group no statistically significant difference was observed ($p=0.141$). There were significant differences in the Amount of Anesthetic Solution (ml) and Duration of the Analgesia Effect (min) between the first and second visits for both injection methods, respectively as $p=0.003$ for NF-TM and $p<0.0001$ for

The Effect of Needle-free Injection System on Dental Injection Pain in Children: A Cross-over, Randomized Clinical Trial

TM-NF groups. The amount of anesthetic solution used for the 1st visit NF injection was $0,91\pm 0,48$ ml and $0,65\pm 0,30$ ml was for the 2nd visit NF injection. These amounts were statistically lower than TM injection in both visits. In the first visit, the mean duration of the analgesia effect in the NF group was 85.00 ± 39.05 min, whereas in the second visit, the mean duration for NF injection was found to be 90.26 ± 43.25 min. In the TM group, the mean anesthesia duration for the first and second visits was 140.00 ± 59.97 min and 130.00 ± 50.74 min, respectively. Regardless of the visit in which it was first applied, the duration of the analgesia effect in the NF group was found to be statistically significantly shorter than in the TM group ($p < 0,001$).

Table 2: Comparison of the 1st visit and 2nd visit measurements for continuous random variables in Needle Free-Traditional Method and Traditional Method - Needle Free

	1 st visit	2 nd visit	p
Wong Baker (WB) Scores			
Needle Free-Traditional Method	4,44±3,28	1,55±0,88	0,056
Traditional Method - Needle Free	1,68±1,91	2,52±2,56	0,119
FLAAC			

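### The finding of no significant Wong-Baker difference rests on two separate within-sequence tests; a crossover analysis of the same data indicates more self-reported pain with the needle-free system

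*Combined protocol and SAP*

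**What the plan says.** Section 3.3 sets out a two-period crossover: "children received both types of injections before filling/pulpotomy treatment on their maxillary primary molars in two separate appointments", at least one week apart. On allocation it says "Type and sequence of administration to each individual were randomly assigned (using a coin". Of the children's history it says "None of the children have undergone any previous dental local anesthetic experience, in order to be not influenced by a positive or negative memory".

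The Statistical Analysis paragraph describes paired t-tests or Wilcoxon tests within groups across the two visits, with significance at p ≤ 0.05. It mentions a repeated measures ANOVA only as the source of the effect size for the post hoc power figure.

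Table 2 gives one paired test per sequence. For NF then TM, "the Wong-Baker scores were 4.44 ± 3.28 and 1.55 ± 0.88 , respectively" (p=0.056). For TM then NF, "the WB score was 1.68 ± 1.91 , while in the Needle-Free anesthesia group, the WB score was 2.52 ± 2.56" (p=0.119). The Results conclude: "In both cases, regardless of the method of anesthesia applied first, no statistically significant difference was found in the two groups".

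**The concern.** A crossover lets the techniques be compared with the visit effect removed. The reported tests do not use that. In the NF-first sequence the paired difference is the technique effect plus any visit effect; in the TM-first sequence it is the technique effect minus the visit effect. Neither test isolates technique. The split also leaves 9 and 19 children in place of 28. Two results that each miss 0.05 are then read as one finding about technique.

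Section 3.3 treats memory of an earlier injection as something to be avoided, yet at visit 2 every child has had one injection in the trial. The randomised visit-1 comparison is the only one in children with no earlier dental injection, and it is not reported.

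The trial's title question is injection pain, and its conclusion on self-reported pain is at stake.

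**Working it through.** **Inputs.** Wong-Baker means, SDs and paired p-values come from Table 2. Sequence sizes come from Table 3: NF-TM 6+3=9, TM-NF 12+7=19. Tests are taken as two-sided, since sidedness is not stated.

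**1. SD of the within-child differences.** These are not printed, so they are recovered from the paired-t p-values by SD = d√n/t.
- NF-TM: d = 4.44−1.55 = 2.89; p=0.056 on 8 df gives t=2.233; SD = 2.89×3/2.233 = 3.88.
- TM-NF: d = 2.52−1.68 = 0.84; p=0.119 on 18 df gives t=1.637; SD = 0.84×√19/1.637 = 2.24.

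**2. Period-adjusted crossover estimate.** With technique effect τ and visit effect π, the two differences (NF minus TM) estimate τ+π and τ−π, so their average removes π.
- Estimate: (2.89+0.84)/2 = 1.865.
- Pooled variance: (8×3.88²+18×2.24²)/26 = 8.10 (unrounded SDs).
- SE = ½√[8.10(1/9+1/19)] = 0.576; t = 3.24 on 26 df; p=0.003; 95% CI 0.68 to 3.05.
- Unequal variances: SE = ½√(1.674+0.263) = 0.696; t = 2.68 on 10.6 df; p=0.022; 95% CI 0.33 to 3.40.

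**3. Check against a printed figure.** The visit effect is (2.89−0.84)/2 = 1.025, with t = 1.78. Its partial eta squared is 1.78²/(1.78²+26) = 0.109. The Statistical Analysis paragraph prints 0.108, which supports the recovered SDs. The same formula for technique gives 3.24²/(3.24²+26) = 0.29. The printed effect size, and the 0.94 power built on it, therefore appear to describe the visit effect and not NF versus TM.

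**4. Visit 1 only, NF (n=9) vs TM (n=19).**
- Difference: 4.44−1.68 = 2.76.
- Welch SE = √(3.28²/9+1.91²/19) = √(1.195+0.192) = 1.178; t = 2.34 on 10.7 df; p=0.040; 95% CI 0.16 to 5.36.
- Visit-1 scores rebuilt to fit the Table 4 medians and quartiles give Mann-Whitney p of about 0.02.

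**5. Carry-over contrast.** Two-visit totals: (4.44+1.55)−(1.68+2.52) = 5.99−4.20 = 1.79. The SDs of the totals follow from 2(SD₁²+SD₂²)−SD_diff², giving 2.83 and 3.92. The pooled SE is 1.466; t = 1.22; p=0.23; 95% CI −1.2 to 4.8.

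**6. FLACC by the same steps.** Period-adjusted: (0.67+0.47)/2 = 0.57, 95% CI 0.16 to 0.98, p=0.008 (unequal-variance p=0.028). Visit 1: 0.78−0.21 = 0.57, 95% CI −0.28 to 1.42, Welch p=0.16.

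**7. Scale.** Section 3.3.3 gives Wong-Baker as 0 to 5. With mean 4.44 and n=9, the largest SD possible on that range is √(4.44×0.56×9/8) = 1.67. Table 2 prints 3.28, and Table 4 prints a quartile of 9.5.

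**The case against.** The Results sentence is literally true of the two tests it summarises, and it says only that significance was not reached. The visit-1 test is post hoc, has nine NF children, and its interval starts near zero. At visit 1 FLACC is not significant. All of this stands. It is why visit 1 should be a sensitivity result, and why the case rests mainly on the crossover estimate.

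Loss of naivety at visit 2 is inherent in any crossover of first-time experiences. This also stands. A reader might infer that half the ratings breach an eligibility rule. The documents do not support that: section 3.2 lists no such criterion, and the sentence in 3.3 reads naturally as a description of the children before the trial.

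A reader might also infer that memory of the first injection hid the difference, since the NF-TM gap is 2.76 at visit 1 and 2.52−1.55 = 0.97 at visit 2. But 2.76−0.97 = 1.79 is the carry-over contrast itself (p=0.23), so the gap is no separate evidence.

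Nor do the within-child correlations implied by the printed p-values help (about −0.61 for NF-first, +0.53 for TM-first). In NF-first scores rebuilt from Tables 2 and 4, TM takes only two values, seven 2s and two 0s. The correlation depends on where the two zeros fall, and 3 of the 36 placements give one this extreme (p=0.083). A Fisher z comparison is not reliable there.

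**Conclusion.** The point holds as an analysis error that affects the pain conclusion. Non-significance came from splitting 28 children into two tests in which technique and visit are confounded. Combined and adjusted for visit, the same data give about 1.87 points more self-reported pain with NF (95% CI 0.68 to 3.05; 0.33 to 3.40 with unequal variances). Visit 1 agrees in direction, at 2.76 (0.16 to 5.36). Period-adjusted FLACC agrees too; visit-1 FLACC has the same sign but is not significant.

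This rests on the printed p-values being two-sided paired t-tests, as the Table 2 footnote indicates apart from sidedness, and on t-methods for a skewed ordinal score. The crossover estimate also assumes equal carry-over. The data neither show nor exclude unequal carry-over, so they do not support saying that memory masked the difference or that visit 1 should replace the crossover analysis. Point sizes are on the scale used in the tables; a linear rescaling would leave the p-values unchanged.

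**What to change.** - Make the period-adjusted two-sequence analysis of all 28 children the main result for Wong-Baker and FLACC, with 95% CIs, run on the individual data and with an unequal-variance or rank-based check.
- Report the visit-1 NF minus TM difference and CI for both scales as a post hoc sensitivity analysis free of carry-over. State that visit-1 FLACC is not significant.
- Give the carry-over contrast with its CI for description only, and not as a pre-test that chooses the analysis.
- Replace the Results sentence on order of method with these estimates.
- Limit the memory statement in section 3.3 to visit 1.
- Reconcile the Wong-Baker range in section 3.3.3 with the scores in the tables.

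The cost is a little extra analysis of existing data and some rewording. The visit-1 interval will be wide, because it compares 9 children with 19.
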